8.7 Clinical Laboratory Tests

Clinical laboratory tests, performed at the times specified in [Appendix A](#), will consist of the following:

- Thyroid panel (TSH, free T4, and free T3);
- Hematology assessments (WBC count and differential, hemoglobin, hematocrit, and platelet count);

- Coagulation parameters (activated partial thromboplastin time, INR, and prothrombin time); and
- Chemistry assessments (fasting glucose or glycated hemoglobin, creatinine, blood urea nitrogen, sodium, potassium, calcium, chloride, phosphorus, bicarbonate, AST, ALT, GGT, alkaline phosphatase, total bilirubin [or fraction of direct bilirubin if $>1.5 \times \text{ULN}$], albumin, total protein, LDH, CK [or fraction of CK-MB if $>1.5 \times \text{ULN}$]; and cystatin-C).

Urinalysis, performed at the times specified in [Appendix A](#), will evaluate the following kidney biomarkers: KIM-1, NGAL, microalbumin, creatinine, and albumin/creatinine ratio and will evaluate microscopic evaluation of sediment, including cylinders, erythrocytes, and leukocytes.

Pregnancy tests, both urine and serum, will also be performed.

All standard blood and urine tests will be performed by a clinical reference laboratory. Laboratory certification and normal reference ranges for all laboratories used during the study will be on file with the Sponsor prior to study initiation.

The Investigator must review and sign all laboratory test reports. Abnormal screening laboratory tests may be repeated at the discretion of the Investigator. The Investigator is expected to review all clinical laboratory results within a reasonable period of time.

The specific analytes to be measured are listed in [Appendix B](#).

8.8 Vital Signs

Vital signs will include systolic and diastolic blood pressure, heart rate, respiratory rate, and temperature.

Vital signs will be measured at study visits and time points specified in Appendix A using a standardized process. Prior to measuring vital signs, the patient should be sitting for a minimum of 5 minutes with back supported, feet flat on the floor, and measurement arm supported so that the midpoint of the manometer cuff is at heart level.

An automated blood pressure device with digital read-out and an appropriately sized cuff with the bladder centered over the brachial artery should be used for vital sign measurement.

The arm used for the measurement should be recorded. Whenever possible, the same arm should be used for all vital sign assessments throughout the study.

Blood pressure should be recorded to the nearest whole number on an automated device.

Unscheduled vital signs will be collected at any time during the study that a patient experiences any symptoms suggestive of hemodynamic instability.

8.9 Electrocardiograms

Twelve-lead ECGs will be performed in triplicate approximately 1 minute apart after the patient has been resting in the supine position for at least 10 minutes. Each ECG will include all 12 standard leads and will be recorded at a paper speed of 25 mm/sec. The ECG will be performed at times specified in [Appendix A](#). ECGs will be analyzed locally. The following ECG parameters will be recorded:

- PR interval;
- QRS interval;
- Heart rate;
- RR interval;
- QT interval;
- Corrected QT interval (QTc); and
- QTc using Fridericia's correction.

All ECGs must be evaluated by a qualified Investigator for the presence of abnormalities.

8.10 Physical Examinations

A physical examination will include a full neurologic examination, as well as an assessment of general appearance, skin, eyes, ears, nose, throat, neck, lymph nodes, chest, heart (including auscultation for heart sounds and murmurs), abdomen, extremities, and musculoskeletal systems. A physical examination will be performed at the times specified in [Appendix A](#).

9 STATISTICS

9.1 Analysis Populations

The Safety Analysis Set (SAF) will include all patients who receive at least 1 dose of study drug. The SAF will be used for the summary of patient characteristics and safety analyses.

The Full Analysis Set (FAS) will include all patients who receive at least 1 dose of study drug. The FAS is identical to the SAF. The FAS will be used primarily for the analysis of tumor response and other efficacy-related data.

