2 STUDY OBJECTIVES

2.1 Primary Objectives

The primary objective for the dose escalation phase is as follows:

- To evaluate the safety, tolerability, dosimetry, and PD of ascending doses of CAM-H2 in patients with advanced/metastatic HER2-positive breast, gastric, and GEJ cancer, including determination of dose-limiting toxicity (DLT), maximum tolerated dose (MTD), and recommended dose for Phase 2 (RDP2).

The primary objectives for the dose expansion phase are as follows:

- To evaluate the proportion of patients achieving an objective response (complete response [CR] or partial response [PR]) with the use of CAM-H2 as measured by the Response Evaluation Criteria in Solid Tumors (RECIST) version 1.1 (all patients with extracranial lesions) or as measured by the Response Assessment in Neuro-Oncology Brain Metastases (RANO-BM) (patients with brain metastases without extracranial lesions);
- To measure the clinical benefit rate (CBR) of CAM-H2 using the equation $CBR = CR + PR + \text{stable disease (SD)}$, as measured by RECIST version 1.1 (all patients with extracranial lesions) or as measured by RANO-BM (patients with brain metastases without extracranial lesions); and
- To evaluate the safety and tolerability of CAM-H2 in patients with advanced/metastatic HER2-positive breast, gastric, and GEJ cancer.

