2.2 Secondary Objectives

The secondary objectives are as follows:

- To assess the CB of CAM-H2 by evaluating the proportion of patients with a CR, PR, and SD in the dose escalation phase;
- To assess duration of response (DoR);
- To evaluate progression-free survival (PFS) from the time of enrollment in the study to progression of disease or death;
- To measure median OS;
- To evaluate intra- and inter-patient dosimetry and PD of CAM-H2 (dose escalation phase only); and
- To assess for the development of anti-drug antibodies (ADAs).

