Staggered dosing will be applied for all cohorts during dose escalation. The first dose of the first patient of each cohort will be administered at least 2 weeks before the first dose of the next 2 patients (sentinel dosing). Once the MTD or RDP2 has been established, 3 additional patients will be enrolled to receive the MTD or RDP2. The patients treated at the MTD or RDP2 in the dose escalation phase will be included in the readout for efficacy. The dose escalation will be done via increases of the nominal activity of CAM-H2 in cohorts of 3 to 6 patients until approximately 15 (or a maximum of 18) patients have been dosed. The actual dose levels administered to the patient can have a tolerance window of $\pm 10\%$ of the prescribed nominal activity.

Dose escalation will be decided based on a review of all the available safety data obtained after completion of Cycle 1 (ie, after 2 IV administrations) of each dose level. If a patient is not able to complete a full cycle due to AEs related to study drug administration, he/she will not be replaced, and the dose escalation rules will be followed.

In the instance that a patient is not able to complete a full cycle due to AEs not related to study drug administration or due to a negative PD distribution scan, he/she will be replaced to ensure safety data spanning a full treatment cycle can be considered for dose escalation.

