9.2 Statistical Methods

9.2.1 Analysis of Efficacy

Efficacy analyses will be performed on the FAS. Overall response rate (ORR) will be assessed for each patient as well as the CBR, DoR, and PFS. A water-plot analysis of breast cancer and gastric/GEJ cancer populations will be done. Response magnitude, including CR and near-CR (defined as a >90% confirmed tumor volume reduction) will also be considered.

The primary and secondary efficacy variables are described in [Sections 7.1](#) and [7.2](#), respectively.

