9.2.4 Sample Size Determination

The proposed study is a dose escalation (Phase 1) study with an expansion cohort reaching into dose expansion (Phase 2). No formal sample size calculation was performed for dose escalation (Phase 1) of the study. A maximum of 18 patients are planned for dose escalation.

No formal sample size calculation was performed for dose expansion (Phase 2). However, a planned sample size of 52 patients is deemed sufficient to obtain an initial estimate of response rates to formally power a subsequent Phase 2/3 study.

For each indication (ie, breast, gastric, or GEJ cancer), an interim evaluation of efficacy will be conducted when approximately 50% of patients complete Cycle 1 at the recommended dose for expansion based on objective responses determined from RECIST 1.1 or RANO-BM. One analysis will be performed for patients with breast cancer, and another analysis will be performed for patients with gastric or GEJ cancer. If the ORR is <10% for a specific indication (ie, breast or gastric/GEJ), the study will be terminated for that particular indication.

The Statistical Analysis Plan will provide more details on the exact statistical approach.

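### Sections 9.1 and 9.2.1 assign efficacy to all dosed patients with no limit or split by dose or phase, although other sections place the primary ORR and CBR at the dose taken forward

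*Combined protocol and SAP*

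**What the plan says.** Section 9.1 defines the analysis set: "The Full Analysis Set (FAS) will include all patients who receive at least 1 dose of study drug". It adds: "The FAS is identical to the SAF". Section 9.2.1 then says: "Efficacy analyses will be performed on the FAS". It refers to Sections 7.1 and 7.2 for the endpoints, and those sections name no dose or phase either. No other efficacy set is defined.

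Other sections describe a narrower population for the primary endpoints:

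- Section 2.1 lists ORR and CBR under the words "The primary objectives for the dose expansion phase are as follows". Section 3.1.2.2 gives expansion patients the RDP2.
- Section 2.2 makes clinical benefit in escalation a separate, secondary objective: "To assess the CB of CAM-H2 by evaluating the proportion of patients with a CR, PR, and SD in the dose escalation phase".
- Section 3.1.1.2 says which escalation patients join them: "The patients treated at the MTD or RDP2 in the dose escalation phase will be included in the readout for efficacy".
- Section 3.1.2.1 sets a total of at least 52 patients at the dose taken forward.
- Section 9.2.4 bases the interim efficacy evaluation on patients at the recommended dose.

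Section 9.2.4 ends: "The Statistical Analysis Plan will provide more details on the exact statistical approach". The supplied text contains no separate SAP.

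**The concern.** The statistical section and the design sections do not name the same patients. If every dosed patient already counted for efficacy, the sentence in 3.1.1.2 that brings in escalation patients at the MTD or RDP2 would have nothing to do. The interim and final ORR could also rest on different populations, since only the interim is tied to the recommended dose.

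The consequence is a matter of interpretation. Section 9.2.4 says the response rates are meant to help power a later Phase 2/3 study. Section 1.3.1 ties potential efficacy to radioactive content, and the planned levels run from 2 × 50 to 2 × 200 mCi, a fourfold range. A rate that mixes those levels would not describe the dose taken forward.

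**Working it through.** **Plan's own figures.** The 52 has no formal calculation behind it, so there is nothing to reproduce. The escalation size can be counted: 4 levels × 3 patients + 3 added at the selected dose = 15. This agrees with the plan to continue "until approximately 15 (or a maximum of 18) patients have been dosed".

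**Inputs.** Escalation size is 15 to 18 (Section 3.1.1.2). Escalation patients at the RDP2 are taken as 6 to 9: a cohort of 3 or 6, plus the 3 added under Section 3.1.4.2. If the MTD and RDP2 differ and those 3 go to the MTD, only 3 may be at the RDP2. If escalation stops early, only 3 patients may be at another level. All response rates below are assumptions.

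**Patients at other levels.** 15 − 9 = 6; 15 − 6 = 9; 18 − 9 = 9; 18 − 6 = 12; and 18 − 3 = 15 in the case with 3 at the RDP2.

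**Share of the FAS = other / FAS.** Case A counts RDP2 escalation patients within the 52, as the total in 3.1.2.1 does. Case B takes the 52 in 9.2.4 as expansion patients only.

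| Situation | Case A | Case B |
|---|---|---|
| 3 at another level (early stop) | 3/55 = 5.5% | 3/61 = 4.9% |
| 6 at other levels | 6/58 = 10.3% | 6/67 = 9.0% |
| 12 at other levels | 12/64 = 18.8% | 12/70 = 17.1% |
| 15 at other levels (3 at RDP2) | 15/67 = 22.4% | 15/70 = 21.4% |

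The share is also the relative fall in a rate if nobody at another level responds.

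**Effect on a rate, Case A.** Pooled rate = (responders among 52 + n_other × rate elsewhere) / (52 + n_other). The illustrations are ORR 10/52 = 19.2% (exact 95% CI 9.6% to 32.5%) and CBR 26/52 = 50.0% (35.8% to 64.2%).

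| Rate at other levels | n_other | ORR | CBR |
|---|---|---|---|
| None | 6 | 10/58 = 17.2% | 26/58 = 44.8% |
| None | 12 | 10/64 = 15.6% | 26/64 = 40.6% |
| None | 15 | 10/67 = 14.9% | 26/67 = 38.8% |
| Half | 6 | (10 + 6 × 0.096)/58 = 18.2% | (26 + 6 × 0.25)/58 = 47.4% |
| Half | 12 | (10 + 12 × 0.096)/64 = 17.4% | (26 + 12 × 0.25)/64 = 45.3% |
| Equal | any | 19.2% | 50.0% |
| Double | 3 | (10 + 3 × 0.385)/55 = 20.3% | not illustrated |

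With 12 patients elsewhere and no response among them, the falls are 19.2 − 15.6 = 3.6 points for ORR and 50.0 − 40.6 = 9.4 points for CBR. With 15 they are 4.3 and 11.2 points. Every pooled value in the table lies inside the interval for the 52.

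**Not counted.** The 52 is a minimum. Patients replaced after a negative PD distribution scan stay in the SAF (Table 1, footnote 1) and so in the FAS. Rates by indication cannot be worked out because counts by indication are not given.

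**The case against.** The strongest reply is that Section 9 defines who is eligible for efficacy analysis and never says that dose levels share one denominator. An all-treated FAS, subset to suit each phase's objective, is an ordinary arrangement, and objective 2.2 needs the escalation patients in it. The intended primary population can largely be assembled from Sections 2.1, 3.1.1.2, 3.1.2.1 and 3.1.2.2, and denominators by endpoint are usual SAP content. All of this stands. A reader might infer that the protocol prescribes a single pooled ORR and CBR across all activity levels. The text does not support that. It leaves pooling open by setting neither a restriction nor a split.

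A reader might also infer that a decision is at risk. The documents do not support that either. The only efficacy rule with a consequence, termination of an indication when ORR is below 10%, is already confined to the recommended dose. There is no hypothesis test and no success criterion.

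Nor is dilution established. Levels above the RDP2 may have been tested, and the documents give no response rates by level, so a mixed rate could move either way.

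What the reply does not remove is the conflict. Section 9.1 states a rule on population that differs from the one the design sections describe, and a SAP written to Section 9.1 would inherit it.

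Two related matters are only clarifications: whether the 52 in 9.2.4 includes RDP2 escalation patients, and who counts if the MTD and RDP2 differ.

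**Conclusion.** The point holds as a minor inconsistency in the protocol text. Sections 9.1 and 9.2.1 do not carry over the population that the rest of the protocol indicates for the primary ORR and CBR.

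Its size is conditional. If the FAS serves as one denominator, other levels make up roughly 5% to 19% of it under the main assumptions, and about 22% with only 3 escalation patients at the RDP2. These are ranges under stated counts, not firm limits. The illustrated shifts rest wholly on assumed response rates. What would suffer is the meaning of the estimate carried into planning the next study. Whether the SAP already resolves the matter is unknown.

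**What to change.** In Sections 9.1/9.2.1, state that primary ORR and CBR are estimated in all patients who received at least 1 dose at the RDP2, meaning expansion patients plus escalation patients at that dose. Apply the same set to DoR, PFS and OS when they are reported for the dose taken forward. Report the other escalation levels separately by dose, which serves objective 2.2. Keep the all-dosed set for safety.

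For clarity, make 9.2.4 agree with 3.1.2.1 on what the 52 includes, say which escalation patients count if the MTD and RDP2 differ, and carry the wording into the SAP.

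This takes a few sentences and no new data. The cost is a smaller denominator and a slightly wider interval: for example 32.5 − 9.6 = 22.9 points for 10/52, against 30.5 − 10.1 = 20.4 points for 12/64.

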9.2 Statistical Methods

9.2.1 Analysis of Efficacy

Efficacy analyses will be performed on the FAS. Overall response rate (ORR) will be assessed for each patient as well as the CBR, DoR, and PFS. A water-plot analysis of breast cancer and gastric/GEJ cancer populations will be done. Response magnitude, including CR and near-CR (defined as a >90% confirmed tumor volume reduction) will also be considered.

The primary and secondary efficacy variables are described in [Sections 7.1](#) and [7.2](#), respectively.

9.2.2 Analysis of Dosimetry

Dosimetry for CAM-H2 via SPECT/CT and planar WB scans will be assessed as described in [Section 7.4.6](#).

All dosimetry evaluations will be done using the OLINDA/EXM or equivalent software. Total dose estimates and the dose estimate for the organs with the highest dose (most likely the kidneys or liver) will be reported using classical descriptive statistics for continuous variables (N, mean, median, standard deviation, minimum, and maximum).

9.2.3 Analysis of Safety

Safety analyses will be performed on the SAF. Descriptive statistics will be used for all safety parameters.

Safety and tolerability will be assessed during the study and will include the incidence and severity of TEAEs, MTD of CAM-H2, DLT rate of CAM-H2, RDP2 for CAM-H2, physical examinations, vital signs, clinical laboratory tests, urinalysis, dosimetry results, and concomitant medications as described in [Section 8](#).

AEs will be coded using the most current version of the Medical Dictionary for Regulatory Activities. TEAEs will be summarized by system organ class and preferred term. TEAEs will be further classified by maximum severity and relationship to treatment. A list of SAEs, AEs leading to withdrawal from the study, and AEs leading to death will be provided.

Summary statistics for laboratory values will be provided at baseline, post-baseline, and for changes from baseline to post-baseline by treatment. Vital signs and ECG parameters will be summarized similarly. The occurrence of laboratory abnormalities will be summarized by treatment. Physical examination data will be listed.

Concomitant medications will be coded using the most current version of the WHO Drug Dictionary. Concomitant medication data will be summarized by treatment. Concomitant medication data and prior medications will be listed.

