1.3.2 Dosimetry Rationale

The proposed dose escalation of radioactivity is based on dosimetry extrapolations obtained in the dosimetry study in non-human primates using the study drug. The proposed dose escalation is described in [Section 5.1](#).

Dosimetry analysis predicts that the dose-limiting organ will be the kidneys. The calculations show that the kidneys receive a mean absorbed radiation dose of 34.9 ± 2 mGy/mCi (or 0.94 ± 0.05 mGy/MBq) in male subjects (the most sensitive sex) when Vamin® 18 Electrolyte Free, an amino acid solution, is administered. The absorbed dose limit for the kidneys is 23 Gy.¹¹ Above this level, radiotoxicity could occur. As a result, it is estimated that significant kidney toxicity is unlikely to occur at levels up to 659 mCi (24.1 GBq) of CAM-H2. For the highest intended dose of 2×200 mCi, the estimated kidney dose is 14 Gy.

Red bone marrow is the most radiosensitive tissue in the body. CAM-H2 results in a red bone marrow exposure of 2.2 ± 0.5 mGy/mCi (or 0.059 ± 0.001 mGy/MBq) in male subjects, based on modeling. The absorbed dose limit for bone marrow is 2 Gy.¹¹ Above this level, significant hematotoxicity is expected. This level of irradiation would only occur at 909 mCi (33.6 GBq) of CAM-H2 in a single dose. Therefore, severe hematotoxicity is unlikely to occur at the doses of CAM-H2 in the current study (100 to 400 mCi). CAM-H2 at a therapeutic cumulative dose of 400 mCi (14.8 GBq) would deliver 0.88 Gy to the red bone marrow.

The dosimetry data for CAM-H2 indicate that CAM-H2 is unlikely to present clinically relevant radiotoxicity to healthy tissues up to the level of 14.8 GBq (2×200 mCi) administered in 1 cycle.

In order to mitigate the risk of kidney radiation injury, an amino acid infusion consisting of arginine and lysine will be administered from 30 minutes before study drug administration to 3 hours after study drug administration, a method routinely used in targeted radionuclide therapy (eg, Lutathera® [Novartis]). Preclinical studies with CAM-H2 show that infusion of arginine and lysine reduces kidney retention levels by approximately 40%.

See Section 7 of the Investigator's Brochure for a detailed description of the justifications.

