3.1.1.2 CAM-H2 administration

In the dose escalation phase, all patients will receive at least 1 cycle of CAM-H2. Patients with CB may receive up to 4 cycles of CAM-H2, as long as the cumulative kidney dose remains <23 Gy (based on the dosimetry results during Cycle 1). Cycles will be given as 2 IV administrations, 4 weeks apart. However, if a patient misses a dose of study drug due to study drug production problems or due to other circumstances (in certain cases), the interval between doses may be extended up to 6 weeks (Cycles 1 and 2) or up to 12 weeks (Cycles 3 and 4) (see [Section 3.1.5.3](#)).

Patients will be admitted to a radioactive unit for hospitalization during each IV administration for a total of 48 hours. This hospitalization can be shortened if ^{131}I decay and the patient's clearance allow discharge according to the applicable local regulations on radioactive compound exposure. Ancillary treatments to be given with CAM-H2 include thyroid-blocking drugs, premedication therapy (anti-emetic, anti-histamine, and anti-pyretic therapy), saline infusion, and amino acid infusion.

Cycle 1 will consist of the following:

- Dose 1 of CAM-H2: Visit 3 (Week 0);
- Safety Follow-Up Period: Visit 4 (Week 1), Visit 5 (Week 2), and Visit 6 (Week 3);
- Dose 2 of CAM-H2: Visit 7 (Week 4); and
- Safety Follow-Up Period: Visit 8 (Week 5), Visit 9 (Week 6), Visit 10 (Week 8), and Visit 11 (Week 11) (EOT Visit or Cycle 2 eligibility assessment).

If the patient has CB, and the cumulative kidney dose remains <23 Gy (based on the dosimetry results during Cycle 1), a second cycle may be initiated within 2 weeks after Visit 11 (Week 11) of Cycle 1, once the necessary Visit 11 (Week 11) safety follow-up assessments have been completed and reviewed. If the patient does not have CB, no further treatment will be administered and the patient will enter the long-term follow-up period.

If the patient has CB, Cycle 2 will then be initiated as follows:

- Dose 1 of CAM-H2: Visit 12 (Week 0);
- Safety Follow-Up Period: Visit 13 (Week 1), Visit 14 (Week 2), and Visit 15 (Week 3);
- Dose 2 of CAM-H2: Visit 16 (Week 4); and
- Safety Follow-Up Period: Visit 17 (Week 5), Visit 18 (Week 6), Visit 19 (Week 8), and Visit 20 (Week 11) (EOT Visit or Cycle 3 eligibility assessment).

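### Crude adverse event and laboratory-abnormality percentages compared across dose levels mix unequal numbers of cycles and can attenuate a dose-toxicity trend

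*Combined protocol and SAP*

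**What the plan says.** Section 9.2.3 of the protocol plans descriptive safety statistics on the Safety Analysis Set. TEAEs are tabulated by coded class and term, and "TEAEs will be further classified by maximum severity and relationship to treatment". For laboratory data, "The occurrence of laboratory abnormalities will be summarized by treatment". The section defines no TEAE window, by-cycle table or person-time denominator, and it does not ask for the number of cycles received. Section 9.2.4 leaves further statistical detail to a SAP, and the supplied document contains no SAP text.

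Exposure is set in Section 3.1.1.2 for escalation: "Patients with CB may receive up to 4 cycles of CAM-H2, as long as the cumulative kidney dose remains <23 Gy". The gate uses Cycle 1 dosimetry. A patient without clinical benefit stops after the current cycle at any level. Expansion patients may have at most 2 cycles (Section 3.1.2.2).

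Section 1.3.2 supplies the projection: "the kidneys receive a mean absorbed radiation dose of 34.9 ± 2 mGy/mCi" (males, with amino acids), and "The absorbed dose limit for the kidneys is 23 Gy". For the top level, "the estimated kidney dose is 14 Gy" per cycle.

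**The concern.** The escalation phase's primary objective (Section 2.1) is safety and tolerability over ascending doses, so the safety tables will be read across dose levels. A percentage of patients who ever had an event, or a worst grade, rises with time observed and with the number of assessments. If lower levels may stay on treatment longer, they collect more events for reasons unrelated to dose. A real increase with dose then looks weaker, and equal toxicity can look inverse.

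Laboratory tables are the most exposed. Counting the scheduled draws after first dose in Sections 6.2.2 and 6.2.3 gives 10 in Cycle 1 and 8 in each later escalation cycle. Four, three, two and one cycles therefore mean 34, 26, 18 and 10 chances to record an abnormality.

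At the dose chosen for expansion there is a second mixture: escalation patients there may have up to 4 cycles, expansion patients at most 2.

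**Working it through.** **Reproducing the protocol's figures.** 23 Gy / 34.9 mGy/mCi = 659 mCi, and 400 mCi × 34.9 mGy/mCi = 13.96 Gy. Both match Section 1.3.2. (The bracketed 24.1 GBq is slightly low, since 659 × 0.037 = 24.4; this does not affect the point.)

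**Permitted cycles.** Activity per cycle is 100, 200, 300 and 400 mCi (Table 3). Kidney dose per cycle = activity × 34.9 mGy/mCi. Reading A counts the next cycle: the largest n ≤ 4 with n × dose per cycle < 23 Gy. Reading B counts only dose already received: cycle n may start if (n − 1) × dose per cycle < 23 Gy. Scheduled weeks from first dose to the last treatment-period visit = 13(n − 1) + 11, using the full 2-week gap between cycles.

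| | Level 1 | Level 2 | Level 3 | Level 4 |
|---|---|---|---|---|
| Gy per cycle | 3.49 | 6.98 | 10.47 | 13.96 |
| A: cycles | 4 | 3 | 2 | 1 |
| A: weeks | 50 | 37 | 24 | 11 |
| A: total mCi | 400 | 600 | 600 | 400 |
| B: cycles | 4 | 4 | 3 | 2 |
| B: weeks | 50 | 50 | 37 | 24 |
| B: total mCi | 400 | 800 | 900 | 800 |

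With no gap between cycles, A gives 44/33/22/11 weeks. With every permitted missed-dose extension after first dose, the 50-week maximum becomes 50 + 2 + 2 + 2 + 4 × 8 = 88.

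**Sensitivity to dosimetry (reading A).** The cycle counts stay 4/3/2/1 from 32.9 to 36.9 mGy/mCi at nominal activity. They are 4/4/3/2 at 20 mGy/mCi, 4/2/1/1 at 45 and 3/1/1/1 at 60. All levels may have 4 cycles below 23 Gy / (4 × 400 mCi) = 14.4 mGy/mCi. On reading B that threshold is 23 Gy / (3 × 400 mCi) = 19.2 mGy/mCi.

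**Effect when true toxicity is equal.** Assumptions: hazard h = 0.02 per week at every level, and a chance c of continuing after each cycle. The documents give neither figure. Incidence after n cycles = 1 − exp(−h × weeks) = 19.8%, 38.1%, 52.3% and 63.2% for n = 1 to 4. Weights are (1 − c)c^(n−1), with the remainder at the maximum. Example, Level 1, c = 0.5: 0.5 × 19.8 + 0.25 × 38.1 + 0.125 × 52.3 + 0.125 × 63.2 = 34%.

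| c | A: Levels 1/2/3/4 | B: Levels 1/2/3/4 |
|---|---|---|
| 0.3 | 27/27/25/20% | 27/27/27/25% |
| 0.5 | 34/32/29/20% | 34/34/32/29% |
| 1.0 | 63/52/38/20% | 63/63/52/38% |

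At h = 0.01 per week and c = 1.0, A gives 39/31/21/10%.

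**Effect when toxicity rises with dose.** Assumptions: hazard proportional to activity, Level 1 risk 10% per 11 weeks, reading A. The Cycle 1 window shows 10/19/27/34%, a Level 4 to Level 1 ratio of 3.4. Crude whole-treatment incidence shows:

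| c | Levels 1/2/3/4 | Ratio |
|---|---|---|
| 0 | 10/19/27/34% | 3.4 |
| 0.3 | 14/26/34/34% | 2.4 |
| 0.5 | 19/31/39/34% | 1.85 |
| 0.7 | 25/38/43/34% | 1.39 |
| 1.0 | 38/51/50/34% | 0.90 |

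**The case against.** Several objections carry weight.

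- **Time on treatment is not time on study.** A reader might infer that Level 1 is observed for 50 weeks and Level 4 for 11. The documents do not support that: Section 3.1.3 continues AE assessment into follow-up of up to 12 months. For patients without progression the maxima become about 50 + 52 = 102 against 11 + 52 = 63 weeks, a ratio of 1.6 rather than 4.5. With the TEAE window undefined, neither ratio is established. Follow-up does not equalise the periods, because it is added to unequal ones, and its listed procedures include no laboratory tests.
- **Continuation is not universal.** It requires clinical benefit after each cycle, in disease refractory to standard treatment. Section 1.3.1 expects radioactive content to determine efficacy, so low-level patients may stop sooner for lack of benefit, which would offset the imbalance. This is plausible but unquantified. Stable disease counts as benefit, so some continuation is likely.
- **The coefficient is a projection** from non-human primates, in the more sensitive sex. Patients are gated on Cycle 1 dosimetry, and Level 4 is optional.
- **Dose-level tables are inferred.** Section 9.2.3 names no dose breakdown for TEAEs and only treatment for laboratory data. In a one-drug study with an ascending-dose objective, dose level is the natural grouping.
- **Classifying TEAEs by relationship** helps set aside background events. It does nothing for laboratory occurrence, and related events also accumulate over cycles.
- **The SAP may already deal with this.** That cannot be checked here.

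A reader might also infer that dose selection is biased. It is not shown to be: DLTs are confined to Cycle 1 (Section 3.1.4.1), and escalation is decided on data after Cycle 1 (Section 3.1.1.2).

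**Conclusion.** The point holds as a risk of attenuation in the descriptive safety tables. On the protocol's projected dosimetry, lower levels may receive more cycles than the top level under either reading of the gate, and Section 9.2.3 states no safeguard.

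Whether a trend is actually hidden is a stronger claim, and the documents do not support it. With hazard proportional to activity, a true ratio of 3.4 falls to between 2.4 and 1.85 when the chance of continuing is 0.3 to 0.5, and disappears only when nearly everyone continues. With equal hazards of 0.02 per week, the spurious Level 1 to Level 4 difference on reading A is 7 to 14 percentage points at those chances, and 43 only if all continue. On reading B it is 2 to 5 points, and 25 if all continue.

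These sizes rest on assumed hazards and continuation chances and on 34.9 mGy/mCi. The gate creates no imbalance below about 14.4 mGy/mCi. With 3 to 6 patients per level every percentage is imprecise, but that is no reason to add an avoidable bias. DLT rate, MTD and Cycle 1 escalation decisions stand. This is a low-cost improvement to make, not a flaw in dose finding.

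**What to change.** In Section 9.2.3 and the SAP:

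1. Make the dose-level comparison of TEAEs, maximum grade and laboratory abnormalities a Cycle 1 table, from first dose to Visit 11. This is essentially the period already used for DLTs.
2. State the TEAE window. Report all-cycle data over it as events, and as first events, per patient-week of follow-up.
3. Show the number of cycles received and the cumulative administered activity by dose level.

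Separately, the passages on the <23 Gy gate (Sections 3.1, 3.1.1.2, 3.1.2.2, 5.1 and 6.2.3.10, and the schedule footnotes) should be reconciled so that it is clear whether the planned next cycle is counted.

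The cost is protocol and SAP wording and a few extra table shells. Dosing dates and administered activity are already recorded, and no patient procedure changes. The Cycle 1 table leaves out late events, which the all-cycle rates cover.
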